The risk of PNP will be minimized by monitoring the PN with pacing maneuvers before and during the ablation of the right sided PVs. Investigators are encouraged to ensure diaphragmatic capture prior to and post ablation when in the region of the RSPV.

Optimal anti-coagulation prior to procedure, using Heparin to achieve an activated clotting time (ACT) of 350 seconds, during procedure and anticoagulation therapy for 2 months post procedure, can substantially decrease the risk of thrombus formation. Continuous irrigation of the catheter per IFU should reduce the risk.

The risk of ACE will be minimized by implementing an anti-coagulation regimen procedure and during procedure to avoid thrombi/emboli during procedure. Investigators will be instructed to minimize catheter exchange during procedure to mitigate the risk of air introduction. A single transseptal technique is recommended, with administration of heparin bolus prior to transseptal puncture.

To prevent effusion and tamponade, the VARIPULSE™ Catheter should be used as instructed, including ensuring that the loop of the catheter is not turned in a counterclockwise manner while inside of the patient.

To prevent the risk of pulmonary injury, investigators will be instructed to follow the recommended workflow.

To reduce the incidence of heart block the investigators are instructed to follow the recommended workflow.

In accordance with the 2020 ESC AF Management Guidelines[35], all subjects should be maintained on systemic oral anticoagulation therapy for at least two months post-procedure. In addition, the study protocol requires subjects to be on uninterrupted anticoagulation prior to the procedure. After two months post-procedure, a decision regarding continuation of systemic anti-coagulation agents will be based on the subject's risk for thromboembolism.

Finally, safety data will be evaluated periodically by a Data Monitoring Committee (DMC) as described in the DMC Charter. A Clinical Events Committee (CEC) will be implemented to adjudicate the primary safety endpoint events. The CEC will operate as described in the CEC Charter.

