10.2 Eligibility Criteria

Inclusion Criteria

Candidates for this study must meet ALL of the following criteria:

1. Symptomatic paroxysmal AF with:
 - a. At least two (2) symptomatic AF episodes within last six (6) months from enrollment
 - b. At least one (1) AF episode electrocardiographically documented within 12 months prior to enrollment. Electrocardiographic documentation may include, but is not limited to electrocardiogram (ECG); Transtelephonic monitoring (TTM), Holter monitor or telemetry strip, and
 - c. A physician's note indicating recurrent self-terminating AF within 7 days.
2. Failed at least one (1) AAD (Class I or Class III) as evidenced by recurrent symptomatic AF, intolerable side effects to the AAD, or contraindication to the AAD
3. Age 18-75 years
4. Willing and capable of providing consent
5. Able and willing to comply with all pre-, post- and follow-up testing and requirements.

Exclusion Criteria

Subjects will be excluded from the study if they meet ANY of the following criteria.

1. Previously diagnosed with persistent AF (> 7 days in duration)
2. AF secondary to electrolyte imbalance, thyroid disease, or reversible or non-cardiac cause (e.g., untreated documented obstructive sleep apnea and acute alcohol toxicity).
3. Previous surgical or catheter ablation for AF
4. Patients known to require ablation outside the PV ostia and outside the CTI region (e.g., atrioventricular reentrant tachycardia, atrioventricular nodal reentry tachycardia, atrial tachycardia, ventricular tachycardia and Wolff-Parkinson White)
5. Documented severe dilatation of the LA (LAD >50mm) antero-posterior diameter on imaging within 6 months prior to enrollment.
6. Documented LA thrombus by imaging within 48 hours of the procedure.

7. Documented severely compromised LVEF (LVEF <40%) by imaging within 6 months prior to enrollment
8. Uncontrolled heart failure or New York Heart Association (NYHA) Class III or IV
9. History of blood clotting, bleeding abnormalities or contraindication to anticoagulation (heparin, warfarin, or dabigatran),
10. Documented thromboembolic event (including TIA) within the past 12 months
11. Previous PCI/MI within the past 2 months
12. Coronary Artery Bypass Grafting (CABG) surgery within the past 6 months (180 days)
13. Valvular cardiac surgical/percutaneous procedure (i.e., ventriculotomy, atriotomy, valve repair or replacement and presence of a prosthetic valve).
14. Unstable angina within 6 months

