10.4 Subject Withdrawal/Early Termination

Subjects may withdraw from the clinical investigation at any time. The decision for the subject to withdraw informed consent must be made independently of influence by the investigator or site personnel. The subject's decision will be documented in the source and eCRF. The investigator may also choose to withdraw a subject from the study if there are safety concerns. If a subject withdraws from the study, the date for withdrawal will be recorded on the appropriate electronic case report form (eCRF).

All data will be collected (as available) until the subject is withdrawn. If the subject is withdrawn due to an adverse event (AE) or serious adverse event (SAE), the investigator should follow the subject until the AE/SAE has resolved or is considered stable.

Subjects who have signed the ICF but are found to be ineligible PRIOR to insertion of the study catheter will be recorded as screen failures in the eCRF.

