10.6 Subject Disposition

- **Enrolled Subjects:** subjects who sign the study ICF.
- **Excluded Subjects:** subjects who are enrolled but never undergo insertion of the study catheter. Excluded subjects will not be included in the primary endpoint analyses and will only be followed between the time of ICF signature and exclusion from the study for adverse event reporting. Subjects who signed the ICF but are found to be ineligible prior to the procedure will be recorded as screen failures in the eCRFs.
- **Evaluable Subjects:** all enrolled subjects who have the study catheter inserted.
- **Discontinued Subjects:** evaluable subjects who have the study catheter inserted but do not undergo ablation (i.e., no PFA energy is delivered with the study catheter). Discontinued subjects will remain in follow-up for 3 months post catheter insertion. If a SAE is reported for a discontinued subject, the subject will be followed until event resolution (with or without sequelae), stabilization, or until the event is adequately explained.
- **Lost to Follow-up Subjects:** subjects who are evaluable, but contact is lost after most recent follow-up visit (despite 3 documented attempts to contact the subject).
- **Withdrawn / Early Termination Subjects:** subjects who withdraw consent for study participation or are withdrawn/terminated from the study by the investigator prior to completion of all follow-up visits.
- **Completed Subjects:** enrolled subjects who have not been excluded, discontinued, withdrawn, terminated early, or lost-to-follow-up prior to the final study visit and have completed the 12-month follow up visit.

11. Responsibilities

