- **Physical Exam** including standardized neurological examination: Exam should be performed by a physician or equivalent (NP or PA) prior to the ablation procedure. The following items will be evaluated as part of the standardized neurological examination: mental status (e.g. orientation, attention, vision, hearing, speech, level of consciousness), cranial nerve testing, assessment of gait and coordination, ability to move all extremities, and evaluation of sensory and motor strength of all 4 extremities.
- **Vital Signs:** height, weight, pulse rate, body temperature, blood pressure
- **Electrocardiogram:** Data from 12-lead ECG recordings will be collected, if available.
- **Imaging to determine LA size and LVEF:** Imaging is required to determine the atrial size prior to the AF procedure. A **Transthoracic Echocardiogram (TTE)** is allowable imaging modality to determine LA size and LVEF. If the subject has undergone an imaging procedure (CT, MRI or ICE or TEE) within the last 6-months where the atrial size (parasternal long axis view) and LVEF were assessed and documented, the pre-procedure imaging assessment is not required.
- **Imaging for detection of LA thrombus** (performed within 48 hours of the study procedure) or day of ablation procedure). The following are allowable imaging modalities:
 - TEE
 - CT/MRI
 - Intracardiac Echocardiography (ICE)

CCI

CCI

CCI

CCI

- Number of PFA applications
- Ablation locations/targets
- Energy delivered
- PFA application time
- Ablation settings
- Procedure time (from first femoral puncture to last catheterout)
- Mapping time (start mapping - end mapping)
- Total fluoroscopy time
- Device deficiency information (if applicable)

Additional data collection for the Pilot Phase only:

- Heparin usage and dosage
- Post procedure, high resolution photographs of all VARI-PULSE™ catheters used during a procedure (with scale)
- Catheter dwell time

In addition to the data collected on the CRFs, a back-up of the CARTO™3 file and generator data identified with the subject's study number will be made for each case and are required to be sent to the sponsor as part of the data collection.

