Bleeding Complications (ISTH definition):	
Major (ISTH definition):
 
Fatal bleeding AND/OR symptomatic bleeding in a critical area or organ, such as intracranial, intraspinal, intraocular, retroperitoneal, intraarticular, pericardial, or intramuscular with compartment syndrome AND/OR bleeding causing a fall in hemoglobin level of 2 g/dL (1.24 mmol/L) or more, or leading to transfusion of two or more units of blood.
 
Clinically relevant nonmajor bleed (ISTH definition):
 
An acute or subacute clinically overt bleed that does not meet the criteria for a major bleed but prompts a clinical response such that it leads to one of the following: hospital admission for bleeding; physician guided medical or surgical treatment for bleeding; change in antithrombotic therapy (including interruption or discontinuation).
 
Minor bleeding (ISTH definition):
 
All nonmajor bleeds. Minor bleeds are further divided into clinically relevant and not.

Catheter Insertion	Defined as the VARIPULSE™ Catheter breaching the sheath and entering the bloodstream.
Device Deficiency	Inadequacy of a medical device related to its identity, quality, durability, reliability, safety or performance, such as malfunction (failure of a medical device to perform in accordance with its intended purpose when used in accordance with the instructions for use or protocol), misuse or use error and inadequate labeling.
Documented AF/AT/AFL of unknown origin episode	An AF/AT/AFL of unknown origin ⁺ episode documented by an electrocardiographic monitoring tool. This may include ILR, ECG, TTM, Holter monitor, or telemetry strip. Reporting of a symptomatic episode by a patient or in a referral letter is not considered a documented AF episode.
Minor Pericarditis	Pericarditis will be considered 'minor' if it is treated using only analgesics and does not extend hospitalization by more than 48 hours.
Paroxysmal AF	Paroxysmal AF is defined as recurrent AF (≥ 2 episodes) that terminates spontaneously within 7 days. Episodes of AF of ≤ 48 hours duration that are terminated with electrical or pharmacologic cardioversion should also be classified as paroxysmal AF episodes.

Term	Definition
Permanent AF	Not appropriate in the context of patients undergoing catheter ablation of AF; refers to a group of patients where a decision has been made not to pursue restoration of sinus rhythm by any means, including catheter or surgical ablation.

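### No safety contact is scheduled after exclusion for subjects who had vascular access but no VARIPULSE insertion: a minor gap in safety accounting

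*Protocol*

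**What the plan says.** Protocol section 10.6 defines excluded subjects as "subjects who are enrolled but never undergo insertion of the study catheter". They stay out of the primary endpoint analyses and "will only be followed between the time of ICF signature and exclusion from the study for adverse event reporting". Appendix III fixes what insertion means: "Defined as the VARIPULSE™ Catheter breaching the sheath and entering the bloodstream". Neither definition mentions venous access, heparin or transseptal puncture.

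The protocol allows invasive steps before that point. Section 6.4.3 Risk Mitigation says: "A single transseptal technique is recommended, with administration of heparin bolus prior to transseptal puncture". Section 13.2 accepts intracardiac echocardiography as a check for left atrial thrombus, up to the day of ablation. Section 10.2 lists as an exclusion criterion "Documented LA thrombus by imaging within 48 hours of the procedure".

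The screen-failure rule is worded in two ways. Section 10.4 applies it to consented subjects "found to be ineligible PRIOR to insertion of the study catheter". Section 10.6 applies it to those "found to be ineligible prior to the procedure will be recorded as screen failures in the eCRFs".

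A subject whose catheter was inserted but who received no pulsed field energy is called discontinued and is followed for 3 months from insertion (protocol section 10.6). SAP section 4 gives safety as the purpose of that follow-up.

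**The concern.** The follow-up rule turns on one event, entry of the study catheter into the blood. Part of the procedural risk arises before it. Femoral access, anticoagulation and septal puncture can each cause harm that shows itself after the patient has left the laboratory: access-site bleeding, pseudoaneurysm or pericardial effusion. The protocol recognises late onset itself, since it counts tamponade or perforation as a primary adverse event up to 30 days after ablation.

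If a case stops between access and insertion, the subject falls into the group whose follow-up ends at exclusion. At stake are the completeness of the study's overall safety account and a safety contact for a consented patient who has had invasive steps.

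**Working it through.** The plan gives no figure to reproduce. The check compares definitions and then sizes the gap.

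**Step 1: status and follow-up, side by side**

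| Situation | Status (protocol 10.6 with Appendix III) | Scheduled safety follow-up |
|---|---|---|
| Consented, no invasive step | Excluded | Until exclusion |
| Venous access, heparin or transseptal puncture; no VARIPULSE insertion | Excluded | Until exclusion |
| VARIPULSE inserted, no energy delivered | Discontinued | 3 months from insertion |

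The second row follows from the two definitions; the protocol does not describe it in those words. It has the rule of the first row, although its procedural exposure may be close to that of the third.

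**Step 2: can the second row occur?** Yes, on the readable text. Intracardiac echocardiography needs venous access, it is an allowed thrombus check on the day, and a thrombus finding excludes the subject. Section 10.4 also sets its cut-off at catheter insertion, which can fall inside the procedure.

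**Step 3: when does follow-up end?** At exclusion, which no readable passage dates. It could be when the case is abandoned, at discharge, or when the form is completed. The two screen-failure cut-offs in 10.4 and 10.6 do not settle it.

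**Step 4: what else collects events?**
- Section 13.5 requires adverse events to be collected from consent onwards.
- Section 14.1 makes the investigator responsible for events seen by staff or reported by the subject until the study ends, and for those that come to the physician's notice.
- Sections 14.1 and 14.8 require events already open to be followed to a stable outcome.

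None of these schedules a contact after exclusion.

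**Step 5: size.** The documents do not say how many subjects stop between access and insertion, so that share is assumed. The risk ceilings are those in section 6.4.2: below 1% for perforation, below 1% for vessel injury and below 0.5% for anticoagulation haemorrhage. Their sum is 1% + 1% + 0.5% = 2.5%.

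Subjects = N × assumed share. Expected events < subjects × 2.5%.

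- Main phase, N = 248, share 1%: 2.48 subjects; 2.48 × 0.025 = 0.06 events.
- Main phase, N = 248, share 3%: 7.44 subjects; 7.44 × 0.025 = 0.19 events.
- Main phase, wider share 0.5% to 5%: 1.24 to 12.4 subjects; 0.03 to 0.31 events.
- Whole study, N = 20 + 408 = 428, share 0.5% to 5%: 2.14 to 21.4 subjects; 0.05 to 0.54 events.

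These are upper figures for the three event types. They include events that begin before exclusion, which are recorded anyway, and the perforation figure comes from radiofrequency catheter manipulation, which goes beyond access alone.

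**The case against.** The strongest reply is that the general adverse event rules already cover these subjects. Sections 13.5 and 14.1 run from consent, and a pseudoaneurysm or effusion that brings the patient back to the site could be recorded under them. This stands. A reader might infer from 10.6 that late complications go unrecorded; the documents do not support that. They support only that such events are not actively sought, and that the limiting sentence in 10.6 sits uneasily with 13.5 and 14.1.

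A reader might also infer that follow-up stops on the day of the procedure. No readable text says so, because exclusion has no defined date.

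Redaction matters too. A rule for abandoned cases would naturally sit in the ablation-procedure section, which is largely blacked out, and the SAP's analysis-set definitions are also redacted. An exception may exist there, so the point is limited to the readable text.

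It can further be said that drawing the line at exposure to the investigational catheter is coherent in a study of that catheter, so the 3-month rule for discontinued subjects is not a contradiction. That is fair: the contrast is a design choice. But the protocol does not confine its interest to the device. It collects adverse events from consent, and section 14.7 grades relation to the study procedure separately from relation to the device. Seeking procedure-related events after access fits that approach.

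Finally, the expected number of events is very small. This also stands, and it sets the weight of the point.

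**Conclusion.** The point holds as a minor gap. On the readable text, a subject with vascular access but no VARIPULSE insertion is excluded, and no safety contact is scheduled after an exclusion whose date is undefined. New-onset access, bleeding or effusion events may be recorded if they come to light, but nothing prompts anyone to look for them.

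A reader might suppose that the primary safety result is biased. It is not. Section 10.6 keeps excluded subjects out of the primary endpoint analyses, and a primary adverse event counts only after a procedure that used the VARIPULSE catheter and TRUPULSE generator. The hypothesis test, power and success criteria do not change.

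The size is about 2 to 7 main-phase subjects and 0.06 to 0.19 expected events. This rests on an assumed 1% to 3% share and on the protocol's own risk ceilings; across the wider shares shown, the expected number stays below one. The case for acting is that any such event could be serious for the patient and that the remedy is cheap.

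**What to change.** Amend section 10.6 so that adverse event follow-up ends at exclusion only for subjects who had no vascular access. For excluded subjects who did, use one of two existing structures:

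- Continue adverse event reporting through the Day 7-10 call and a contact in the 1-month window. The call alone would not reach the protocol's 30-day tamponade or perforation limit. The 1-month window is Day 23 to 37, so the contact should fall on or after Day 30.
- Or apply the 3-month rule already used for discontinued subjects.

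Either way, count days from the date of vascular access, because these subjects have no catheter insertion date. List them and their events separately, outside the primary analyses. Define the date of exclusion. Reconcile the screen-failure cut-offs in 10.4 and 10.6, and the limiting sentence in 10.6 with the collection rules in 13.5 and 14.1. If the redacted procedure text already covers abandoned cases, a cross-reference from 10.6 would be enough.

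The cost is a short protocol edit and a handful of extra contacts. Treatment, analysis sets, alpha and sample size stay as they are.

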11.1 Investigator Responsibilities

The Principal Investigator is responsible for supervision of all study activities and is ultimately responsible for overall compliance with protocol, GCP, local and regional regulations, and IRB requirements. Many study activities may be formally delegated to support staff, but the Principal Investigator retains responsibility for supervision of all study activities.

Specific responsibilities include:

- Obtaining IRB approval and renewals
- Providing Sponsor with:
 - Written IRB approval letters and IRB approved consent forms,
 - Signed, dated Investigator Agreement,
 - Signed and dated Financial Disclosure form at study outset and any time financial changes occur, for up to one year following completion of the study
 - Curriculum vitae for each Investigator and key research staff member
 - Copy of current medical license for each study investigator, as applicable
- Maintaining an accurate and current Delegation of Authority Log which identifies all individuals authorized to perform work for the study at each site

- Completing appropriate training on the study device and the study protocol prior to enrolling and treating subjects
- Maintaining accurate and current logs for the study as requested by the study team, including but not limited to:
 - Subject screening log
 - Device Accountability log
- Obtaining informed consent (including privacy language) from patients prior to subject participation
- Performing the ablation procedure as described in the protocol
- Complying with the clinical protocol
- Notifying the Sponsor and IRB of adverse events, deaths, device failure/malfunctions and deviations as defined in this protocol and per IRB requirements
- Notifying Sponsor promptly of withdrawal of IRB approval
- Complying with IRB (as applicable) and Sponsor annual report requirements
- Completing eCRFs accurately and as soon as possible after collection of data
- Reviewing and signing designated eCRFs in a timely manner
- Maintaining relevant source documentation and allow Sponsor direct access to perform monitoring and auditing duties
- Immediately notify the Sponsor of any pending Regulatory Authority audits/inspection at the study site and allow access to study records for authorized regulatory entities
- Complete all subject follow-up visits, including efforts to maintain contact with subjects who fail to comply with the follow-up schedule. Before a subject may be classified as 'lost to follow-up', the Investigator or authorized personnel should document 3 attempts to contact the subject.
- Retaining study records as described in Section 20.2. The Sponsor will notify the Investigator when records may be destroyed.
- Preparing a final report and periodic IRB updates as required.

11.2 Sponsor Responsibilities

The Sponsor (Biosense Webster) will be responsible for the following:

- Preparing study documents including but not limited to the protocol, eCRFs and template informed consent
- Completing pre-study site assessments and approvals
- Obtaining approval from FDA and regulatory agencies, as applicable
- Obtain signed study contracts from investigators/hospitals, contract research organizations, or other involved parties.
- Providing protocol and device training to investigators and research personnel, as applicable
- Instructing operators and technicians in the proper use and monitoring of study devices
- Monitoring the study throughout the duration of the investigation
- Securing investigator/site compliance with the protocol and applicable regulations
- Creation and maintenance of eCRF database
- Conducting all communications with regulatory agencies

- Submitting study supplements for regulatory approval (e.g., request for study expansion), as necessary
- Preparing reports summarizing the status of the clinical study no less often than annually, which will be supplied to FDA and to other regulatory agencies, as applicable. Annual reports may also be provided to the Principal Investigator
- Preparing and submitting the final clinical study report to FDA and applicable regulatory agencies
- Having AEs reviewed by the study specific committees and/or study specific reviewers, as required
- Report the results of an evaluation of an unanticipated adverse device effect to FDA within 10 working days after receiving notice of the adverse effect.
- Register the study with ClinicalTrials.com no later than 21 calendar days after enrolling the first subject and submit study results on all pre-specified outcomes, including negative outcomes to ClinicalTrials.gov no later than one year after completion of the primary endpoint (unless an extension has been approved via certification from the Secretary of Health and Human Services). Results submission could be delayed if an extension is granted to the results submission deadline; however, the release of all results on pre-specified outcomes will be hastened if the study is terminated early.

